#### **Objectives:**

- Primary objective:
  - To assess the effect of foam sclerotherapy of the ulcer veins on time to complete VLU healing

- Secondary objectives:
  - o To chart the rate of ulcer healing at 3, 6, 9 and 12 months
  - o To assess the rate of ulcer recurrence
  - To determine the length of time free from ulcers (ulcer-free time) during the first year after randomization
  - o To report health-related quality of life
  - o To describe the side-effects and complications of foam sclerotherapy

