- Foam sclerotherapy: ulcer veins are identified using a linear US probe 7-10Mhz; polidocanol 0.5-1% mixed with gas in a ratio of 1:4 is used to fill the network of refluxing ulcer veins. A total volume of 5-10ml of foam is used per session. Patients are reviewed after 1 week. Foam sclerotherapy may be repeated after one week if the ulcer veins remain patent and the ulcer is not healed. Only two sessions are permitted per lower limb. Following foam sclerotherapy, foam compression is applied
- Ulcer dressing and re-application of compression is performed on a weekly basis until the ulcer is healed
- Following ulcer healing, grade II compression stockings or adjustable compression wraps are prescribed
- After complete healing the patient is followed up monthly by telephone to enquire about ulcer recurrence, and compliance with compression hosiery
- At completion of the study, the patient is reviewed in person

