#### **Documentation:**

- A secure cloud based digital platform will be created
- Upon randomization, the following data will be collected for each participant:
  - o Unique participant number
  - o **Initial visit clinical assessment:** date, age, gender, clinical center, ulcer size in 2 dimensions, ulcer size as measured by Lesionmeter software, ulcer depth (subjective), ulcer location, ulcer side (right or left lower limb), ulcer duration, presence of pedal pulses, ABPI, history of DVT(s), history of venous intervention(s), type of venous intervention (surgery, ablation, foam, stent), date(s) of venous intervention(s), history of diabetes, HbA1C, BMI (weight and height), cardiac failure (including ejection fraction and NYHA classification), other co-morbidities
  - o **Dressings and compression:** type of ulcer dressing and type of compression used; both recorded at each visit
  - Duplex ultrasound findings: details of superficial and deep system reflux and obstruction
  - o **Foam sclerotherapy:** drug used, concentration, gas used, number of injections, foam volumes injected, number of foam sclerotherapy sessions, perforator treatment
  - Follow up visits: date, ulcer healed?, ulcer size in 2 dimensions, ulcer size as measured by Lesionmeter software, ulcer depth (subjective), foam side effects/complications
  - o **Final visit:** ulcer healed?, ulcer size in 2 dimensions, ulcer size as measured by Lesionmeter software, ulcer depth (subjective), foam side effects/complications
  - **Telephone follow up:** date of date, date of recurrence if any, compliance with compression hosiery
  - o **Ulcer photography:** at least one ulcer photograph at the first visit, and one ulcer or ulcer site photograph during the last visit

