#### Statistical and health economic analysis:

A comprehensive statistical analysis plan will be produced by the study statistician Kaplan-Mayer curves will be created for both Group A and Group B, and will be compared for significance

The total number of patients who achieved complete healing in both groups will be compared Analysis of variance or logistic regression analysis could be used to assess the effect of each variable on healing (age, gender, DM, BMI, ulcer size, and method of treatment)

A health economist will support a health economic evaluation of the study results

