## **Expected problems:**

Recruitment: patients meeting inclusion/exclusion criteria; patients refuse to consent to randomization

Loss to follow-up

Operators deviate from protocol

Patient non-compliance with compression

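### A patient who stops attending while the ulcer is still open has no scheduled outcome collection until the final review, because telephone follow-up starts only after healing

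*Protocol*

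**What the plan says.** The Protocol's Methods section sets three kinds of contact.

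- While the ulcer is open: "Ulcer dressing and re-application of compression is performed on a weekly basis until the ulcer is healed".
- Once it has closed: "After complete healing the patient is followed up monthly by telephone to enquire about ulcer recurrence".
- At the end: "At completion of the study, the patient is reviewed in person". No healing condition is attached to this review.

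The Documentation section fixes what each contact records. Follow-up visits capture "date, ulcer healed?, ulcer size in 2 dimensions, ulcer size as measured by Lesionmeter software", and the final visit also records healing status. The telephone contact captures "date of recurrence if any, compliance with compression hosiery", with nothing on whether or when the ulcer healed.

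The primary objective is "To assess the effect of foam sclerotherapy of the ulcer veins on time to complete VLU healing". The End points section adds healing at 3, 6, 9 and 12 months and ulcer-free time. The Statistical and health economic analysis section plans healing curves by group and states: "The total number of patients who achieved complete healing in both groups will be compared".

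The Expected problems section lists "Loss to follow-up" without a remedy. The Sample size calculations section allows 10% for dropout, not split by arm or healing status. The Exclusion from trial section lists non-compliance with the protocol alongside withdrawal of consent.

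**The concern.** Before healing, every outcome observation depends on the patient coming to a weekly visit. The one remote contact in the design is reserved for patients whose primary event has already happened. A patient who stops coming with an open ulcer, whether it then closes at home or care moves elsewhere, is contacted by nobody under the schedule until the end of the study.

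What is at stake is the primary outcome. If the ulcer closes during the gap, a final review can show that it closed but not reliably when. Status at 3, 6 and 9 months goes uncollected, as does the start of any ulcer-free time. If the patient also misses the final review, or has been excluded for non-compliance, the count of healed patients has a gap too. How censored or missing data are analysed can be left to a statistical analysis plan. Whether the data are collected cannot.

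**Working it through.** **1. Contacts set side by side (Methods and Documentation sections)**

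| Patient's state | Scheduled contact | Healing status recorded? |
|---|---|---|
| Unhealed, attending | Weekly visit | Yes |
| Healed | Monthly telephone call | Already known; recurrence asked |
| Unhealed, not attending | None | No |
| Any, end of study | In-person review | Yes, if still in the trial and attending |

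The third row is the gap. No visit is tied to the 3, 6 or 9-month end points, so nothing else fills it. As an example, a patient who leaves at week 4 of a 52-week period has 52 − 4 = 48 weeks without a scheduled outcome contact, and all three intermediate time points fall inside it.

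**2. How many patients**

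From the Sample size calculations section, with 10% dropout:

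- 0.10 × 300 = 30 patients
- 0.10 × 130 = 13 patients

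These are ceilings under the plan's own allowance. The 10% is not divided by healing status and may include withdrawal of consent or loss after healing.

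**3. Possible effect on the healing curves (illustration; the assumptions are not in the Protocol)**

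Assume exponential healing in one arm with the Protocol's control mean of 75.4 days. True healing by 90 days is 1 − exp(−90/75.4) ≈ 69.7%. Let leavers come only from the slower half of healers, depart within the first 52 days (the median is 75.4 × ln 2 ≈ 52) and be censored on leaving. Simulated Kaplan-Meier estimates are:

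| Leavers | Kaplan-Meier at 90 days | Bias at 90 days | Bias at 12 months |
|---|---|---|---|
| 5% | 70.7% | about +1 point | under 0.2 |
| 10% | 71.4% | about +2 points | under 0.2 |
| 20% | 73.8% | about +4 points | under 0.2 |

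This is bias within one arm. If loss is equal in both arms, much of it cancels in the comparison.

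**4. Possible effect on the count of healed patients (illustration)**

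Suppose leavers are counted as not healed, a convention the Protocol does not state, and true healing is equal in the two arms. The spurious difference is then (leavers in B − leavers in A) × true healing among leavers.

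| Leavers, A v B (assumed) | Leavers heal 85% (assumed) | Leavers heal 40% (assumed) |
|---|---|---|
| 5% v 15% | 0.10 × 0.85 = 8.5 points | 0.10 × 0.40 = 4.0 points |
| 8% v 12% | 0.04 × 0.85 = 3.4 points | 0.04 × 0.40 = 1.6 points |
| 10% v 10% | 0 | 0 |

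Both unequal splits average 10% with equal arms, but the splits themselves are invented. Attendance at the final review would shrink every non-zero figure.

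The two illustrations also point in opposite directions. Censoring slow healers overstates healing in the arm that loses them; counting leavers as not healed understates it. The Protocol therefore fixes neither the size nor the sign of any bias.

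**The case against.** The strongest reply is that the schedule is more intensive before healing than after it: weekly visits against monthly calls. An unhealed patient who follows the Protocol is observed closely, and the gap touches only those who break the schedule. That stands, and it limits the point to non-attenders. It does not remove it, because weekly attendance has no fallback and the Protocol itself expects losses.

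Second, the telephone form is consistent with its purpose, since callers reach only healed patients. That is also fair. The missing healing item follows from the call rule and is not a separate fault, but it must change if the rule does.

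Third, the final in-person review already covers every patient. This is true as the Methods section is written. It recovers final status but not the date or the intermediate status, and the exclusion of non-compliant patients may override it. That non-attenders would also miss the final review is plausible, but not documented.

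Fourth, a reader might infer that the loss probably differs by arm, because Group B has no foam and no sham or blinding is described. The documents do not support that. Both arms share the same weekly, telephone and final contacts, the only arm-specific contact is the review one week after foam, and nothing predicts attendance by arm. An indirect route exists: at the planning means, Group B would stay unhealed 75.4 − 64.1 = 11.3 days longer on average, and so longer in the phase without a fallback. That supports possibly, not probably.

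**Conclusion.** The point holds as a gap in data collection. As written, a patient who stops attending unhealed has no scheduled outcome contact until the final review and, depending on how the exclusion rule is applied, perhaps none at all. This affects time to healing, the 3, 6 and 9-month end points, ulcer-free time and, for those who miss the final review, the count of healed patients.

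At most 30 of 300 or 13 of 130 patients are affected, provided the 10% dropout allowance holds. The loss may be related to healing, because the fallback contact begins only at healing, and it is possibly related to arm. The document demonstrates neither.

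A reader might take the 8.5-point difference as the expected bias. It is not. It needs an invented 5% v 15% split, the same 85% healing in leavers as in stayers (which makes the loss unrelated to healing), and an unstated rule that leavers count as not healed. More moderate assumptions give 1.6 to 4 points, and equal loss gives none. On the healing curves, the illustration gives about 1 to 2 points at 90 days in one arm for 5 to 10% leavers, and almost nothing at 12 months.

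This is worth correcting before recruitment, because the remedy is cheap and lost dates cannot be recovered. It does not show that the trial's comparison would be invalid.

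**What to change.** Make three linked changes to the Protocol.

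1. **Methods.** Extend the monthly telephone call to every randomised patient who is not attending weekly visits, healed or not, unless consent to follow-up is withdrawn.
2. **Documentation.** Add healing status and date of healing to the telephone form. Flag these entries as self-reported, and confirm them in person or by photograph where possible.
3. **Exclusion from trial.** Reconcile this section with the follow-up schedule, so that non-compliance ends neither outcome collection nor the final review. Without this change the added calls could be defeated by the exclusion rule.

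The changes concern data collection only and alter no treatment rule. The cost is a few extra calls through a calling system the Protocol already requires, and two form items. The real downside is quality: healing dates reported by telephone are less exact and come from patients who may know their allocation, which is why they need a flag and confirmation.

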### Sample size calculations:

Sample sizes were calculated at 90% power with alpha of 5%

The sample standard deviation of healing time in days was 26, with the 'worst case' recorded standard deviation being 39.4

The weighted average of healing time for compression only was 75.4 (based on N=1787)

The weighted average of healing time for compression + intervention was 47.3 (based on N=758)

This represents a large effect size of treatment and, even with the 'worst case' SD, would require a sample size of 42 - I feel this is optimistic, likely overestimates the effect size of the intervention and would result in an underpowered study

If, like EVRA, a 15% effect size was considered this would make the healing time estimate for compression + intervention 64.1 days, giving a sample size of 255 (using the 'worst case' recorded standard deviation of 39.4)

Allowing for a dropout rate of 10% and protocol violations the target sample size can be 300 set at patients

With the more lenient SD of 26, and the EVRA effect size of 15%, the sample size is 112

Allowing for a dropout rate of 10% and protocol violations the target sample size can be 130 set at patients

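### The stated 90% power is for a comparison of mean healing days; it is not established for the planned Kaplan-Meier comparison, and the target N is not labelled as per arm or total

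*Protocol*

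**What the plan says.** The protocol's section on sample size calculations works entirely in mean days and standard deviations:

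- "Sample sizes were calculated at 90% power with alpha of 5" per cent.
- "The sample standard deviation of healing time in days was 26, with the 'worst case' recorded standard deviation being 39.4" days.
- For a 15% effect against a compression-only mean of 75.4 days, "this would make the healing time estimate for compression + intervention 64.1 days, giving a sample size of 255", using the SD of 39.4. This is raised to a target of 300 for dropout and protocol violations.
- "With the more lenient SD of 26, and the EVRA effect size of 15%, the sample size is 112", raised in the same way to 130.

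It does not say whether any of these numbers is per arm or for the whole trial.

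The objectives section makes time to complete ulcer healing the primary objective, and the end points run to 12 months from randomization. For the analysis, the section on statistical and health economic analysis says: "Kaplan-Mayer curves will be created for both Group A and Group B, and will be compared for significance". It adds a comparison of the numbers healed and a possible analysis of variance or logistic regression of healing on covariates. It plans no comparison of mean healing days and names no test for the curves.

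**The concern.** A sample size in mean days needs an observed healing time for every patient. An ulcer still open at 12 months has none: it cannot contribute to a mean or SD, but it enters a Kaplan-Meier comparison as a censored observation. Power for that comparison depends on the hazard ratio and the number of healings, and the sample size section gives neither. A reader cannot recover the power of the planned analysis from the protocol.

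At stake is how a null result on the primary objective would be read. It would be taken as coming from a 90%-powered trial, although that figure belongs to a test the protocol does not plan and, depending on how N is read, possibly to twice as many patients.

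**Working it through.** **Inputs.** From the protocol: means 75.4 and 64.1 days (difference 11.3), or 75.4 and 47.3 days (difference 28.1); SD 39.4 or 26; power 90%; alpha 5%; dropout 10%; follow-up 12 months. Assumed: two-sided test, 1:1 allocation, log-rank test, and nearly all ulcers healed by 12 months unless stated.

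**Step 1: reproduce the protocol's figures.** n per arm = 2 × (1.960 + 1.282)² × (SD/difference)², with (1.960 + 1.282)² = 10.507.

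- 2 × 10.507 × (39.4/28.1)² = 41.3; stated 42
- 2 × 10.507 × (39.4/11.3)² = 255.5; stated 255
- 2 × 10.507 × (26/11.3)² = 111.3; stated 112

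All three match as per-arm sizes. As totals the requirement would be 84, 512 and 224. One-sided and 80%-power variants do not reproduce the stated figures.

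**Step 2: patients left after 10% dropout.** Read as totals: 300 × 0.9 = 270 and 130 × 0.9 = 117. Read as per arm: 540 and 234 in all.

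**Step 3: the protocol's own means test at those numbers.** Power = Φ(11.3 / (SD × √(4/N)) − 1.96), with N the total analysed.

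- SD 39.4: N = 270 gives Φ(2.356 − 1.96) = 65%; N = 540 gives Φ(3.332 − 1.96) = 92%
- SD 26: N = 117 gives Φ(2.351 − 1.96) = 65%; N = 234 gives Φ(3.324 − 1.96) = 91%

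**Step 4: log-rank, Weibull proportional hazards.** The Weibull shape is solved from SD/mean in the compression-only arm, and HR = (75.4/64.1)^shape. Events for 90% = 4 × 10.507 / (ln HR)². Power = Φ(½ × √events × ln HR − 1.96).

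- SD 39.4: shape 2.00, HR 1.38, ln HR 0.325, about 398 events needed. 270 events give 76%; 540 give 97%.
- SD 26: shape 3.18, HR 1.68, ln HR 0.516, about 158 events needed. 117 events give 80%; 234 give 98%.

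This model shortens the spread along with the mean: the SD in the foam arm becomes 39.4 × 64.1/75.4 = 33.5 days, where the means calculation uses one SD for both arms.

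**Step 5: log-rank, same SD in both arms.** Simulated, 5,000 trials per case, censored at 365 days (simulation error at most about 0.7 percentage points, √(0.25/5000)):

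| Distribution | SD 39.4, N 270 | SD 39.4, N 540 | SD 26, N 117 | SD 26, N 234 |
|---|---|---|---|---|
| Weibull | 50% | 79% | 54% | 82% |
| Gamma | 52% | 80% | 50% | 78% |
| Lognormal | 58% | 86% | 52% | 80% |
| Normal | 56% | 85% | 58% | 86% |

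In round terms, about 50–60% if the targets are totals and about 77–87% if they are per arm.

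**Step 6: fewer healings.** The protocol gives no healed proportion. If only 85% healed (an assumption), the Step 4 figures would fall to 69% and 73% on the total reading, and to 94% and 95% on the per-arm reading.

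**The case against.** A reader might infer that the trial simply lacks the stated power because a log-rank test has replaced a comparison of means. The documents do not support that, for three reasons.

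- The change of test does not by itself push power below 90%. On the total reading, the means test already has only 65%, and the Weibull proportional-hazards log-rank does better (76–80%). On the per-arm reading, the same model gives 97–98%. Much of the apparent shortfall comes from reading a per-arm N as a total.
- An exponential model would give a far worse picture: HR 75.4/64.1 = 1.18, about 1,595 events needed, 27% power at 270 events. But its SD equals its mean, 75.4 days, about twice the protocol's worst case of 39.4. That result comes from replacing the SD, not from changing the test, and it should not be used.
- Loss of power through unhealed ulcers is a possibility that the protocol does not quantify. Under the Weibull models fitted in Step 4, almost nobody remains unhealed at 365 days.

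All three stand. It can also be said that analysis detail is left to a separate statistical analysis plan. That is fair for the name of the test, but the sample size and its 90% are fixed in the protocol, and a later plan cannot change the basis on which they were set.

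What survives is narrower: the 90% was not calculated for the planned comparison. Under the protocol's own assumption of one SD for both arms, the log-rank power is below 90% on either reading of N.

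**Conclusion.** The point holds in this form: 90% power is not established for the Kaplan-Meier comparison, and the unlabelled N makes the gap larger or smaller.

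- **Targets as totals:** about 65% for the means test; log-rank about 50–60% with equal SDs, or 76–80% under Weibull proportional hazards.
- **Targets as per arm:** log-rank about 77–87% with equal SDs, or 96–98% under Weibull proportional hazards.

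These ranges rest on a 15% shorter mean, the stated SDs, two-sided 5%, 1:1 allocation, 10% dropout, a log-rank test and nearly complete healing within 12 months. A lower healed proportion reduces all the log-rank figures. The documents do not allow the stronger statement that the power is certainly below 90%, because they fix neither the meaning of N nor the shape of the healing-time distribution.

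**What to change.** In the sample size section:

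1. State whether 255, 112, 300 and 130 are per arm or totals, and which target applies.
2. Recompute for the Kaplan-Meier (log-rank) comparison. State the target hazard ratio, the healed proportion expected by 12 months in Group B, the number of healing events required and the dropout allowance.
3. State the resulting power. If recruitment is already fixed, restate the power at that number and do not claim 90%.

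The cost is a rewritten section and a short calculation. Restating the power needs no extra patients. The drawback is that the stated power may become less favourable, clearly so if the targets turn out to be totals.

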## **Methods:**

- Patients with open venous ulcers (C6) will be assessed by duplex ultrasound scan for
  - o Superficial venous reflux, and identify its source
  - o Evidence of post-thrombotic reflux and/or obstruction, and characterize this
  - o Evidence of refluxing "ulcer veins" and/or pathologic incompetent perforators in the vicinity of the VLU

- Cross sectional or invasive venography +/- intravascular ultrasound at the discretion of the treating physician, based the upon suspicion of proximal venous outflow obstruction
- Patients with open VLU and/or refluxing ulcer veins and/or pathologic incompetent perforators will be eligible for admission to the study
- Individuals meeting inclusion criteria will be offered a participant information sheet
- Written informed consent will be obtained
- Consented patients will be randomized into two groups:
  - o Group A: Foam sclerotherapy for ulcer veins in addition to appropriate therapy
  - o Group B: Appropriate therapy alone without foam sclerotherapy for ulcer veins
- Appropriate therapy:
  - Superficial venous pathology only: will be treated by ablation of the superficial venous reflux by surgery or endovenous techniques, in addition to treatment of incompetent leg tributaries by phlebectomy or foam sclerotherapy.
  - O Superficial venous reflux associated with deep venous obstruction or reflux: treatment of the superficial venous reflux will be individualized and left to the discretion of the vascular surgeon in charge.
  - Deep venous obstruction and / or reflux: patients with iliac vein obstruction may be considered for iliac vein stenting. Otherwise, patients with deep venous pathology will be treated by compression.
- In all participants, the VLU will be debrided as clinically indicated and, if there is evidence of infection, a course of antibiotics will be prescribed according to the local standard of care
- Compression therapy will be provided by trained personnel according to the local standard of
  care. Multilayer elastic compression (two to four layers), short-stretch compression,
  compression stockings, and adjustable compression wraps are all deemed to be acceptable.
   Details of compression types used will be recorded

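### The sample sizes of 255 and 112 are per-group figures carried forward as trial totals, so targets of 300 or 130 patients give about 65% power, not 90%

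*Protocol*

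**What the plan says.** The section on sample size calculations in the Protocol opens with "Sample sizes were calculated at 90% power with alpha of 5" per cent. It then gives its inputs:

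- Spread: "The sample standard deviation of healing time in days was 26, with the 'worst case' recorded standard deviation being 39.4".
- Control mean: "The weighted average of healing time for compression only was 75.4 (based on N=1787").
- Intervention mean from the literature: "The weighted average of healing time for compression + intervention was 47.3 (based on N=758").
- Intervention mean under a 15% effect: "this would make the healing time estimate for compression + intervention 64.1 days".

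Three sizes follow: 42 (literature effect, SD 39.4), 255 (15% effect, SD 39.4) and 112 (15% effect, SD 26). The second is worded: "giving a sample size of 255 (using the 'worst case' recorded standard deviation of 39.4"). The section sets 42 aside as resting on too optimistic an effect. The step from 255 to the target reads: "Allowing for a dropout rate of 10% and protocol violations the target sample size can be 300 set at patients". A parallel sentence takes 112 to 130. The section does not say whether any of these figures is per group or for the whole trial.

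The Methods section fixes the design: "Consented patients will be randomized into two groups".

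**The concern.** A two-sample calculation normally returns the size of one group, and the total is twice that. Here the only allowances named between the calculated size and the target are dropout and protocol violations. If 255 and 112 are per group, then 300 and 130 are about half of what 90% power requires.

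The power claim is central to this protocol. Its Rationale notes that the one earlier randomized comparison of foam recruited too few patients for a meaningful result, and the sample size section rejects the 42-patient scenario to avoid an underpowered study. A halved total would bring that problem back: the planned 10% chance of missing the target effect would become roughly one in three under the section's own assumptions.

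**Working it through.** **Inputs.** All come from the sample size section except the number of groups, which is in Methods.

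- Power 90%, alpha 5%. Sidedness is not stated; two-sided is tried first.
- SD 39.4 or 26 days.
- Literature difference: 75.4 − 47.3 = 28.1 days.
- 15% difference: 75.4 − 64.1 = 11.3 days.
- Two groups. The allocation ratio is not stated; 1:1 is assumed.

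**Step 1: reproduce the stated sizes.** For two means under the normal approximation:

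n per group = 2 × (1.960 + 1.2816)² × SD² / d² = 2 × 10.507 × SD² / d²

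| Scenario | n per group | Two-group total, rounded up per group | Protocol states |
|---|---|---|---|
| SD 39.4, d 28.1 | 41.3 | 84 | 42 |
| SD 39.4, d 11.3 | 255.5 | 512 | 255 |
| SD 26, d 11.3 | 111.3 | 224 | 112 |

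All three stated figures match the per-group column. With the unrounded 15% difference (0.15 × 75.4 = 11.31) the middle row is 255.03, closer still to 255.

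**Step 2: check whether another convention gives them as totals.** Totals in the order of the table:

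- One-sided 5%, 90% power: 68, 418, 182.
- Two-sided 5%, 80% power: 62, 382, 168.
- One-sided 5%, 80% power: 50, 302, 132.
- One-sample, two-sided, 90% power: 21, 128, 56.

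None gives 42, 255 and 112. Of the variants tried, only the two-sided, 90%-power, per-group calculation reproduces them.

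**Step 3: power at the targets, read as trial totals.**

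Power = Φ( d / (SD × √(2/n)) − 1.960 ), with n per group

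- 300 patients less 10% = 270, or 135 per group. At SD 39.4: SD × √(2/135) = 4.796; 11.3 / 4.796 = 2.356; Φ(0.396) = 65.4%.
- 300 patients with no loss, 150 per group, SD 39.4: 70.0%.
- 130 patients less 10% = 117, or 58.5 per group. At SD 26: SD × √(2/58.5) = 4.807; 11.3 / 4.807 = 2.351; Φ(0.391) = 65.2%.
- 130 patients with no loss, 65 per group, SD 26: 69.8%.
- If only 255 or 112 patients in total are evaluable, power is 62.9% or 63.3%.

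The t-test version gives 65.1% and 64.5% at the 10% dropout, so the approximation does not matter.

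**Step 4: what 300 in total can detect.** At 135 per group and SD 39.4, the difference detectable with 90% power is 3.2415 × 4.796 = 15.5 days, and 15.5 / 75.4 = 21%. To have 90% power for 11.3 days with 135 per group, the SD must be at most 11.3 / (3.2415 × √(2/135)) = 28.6 days.

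**Step 5: cross the two SDs.** At the 10% dropout, 300 in total at SD 26 gives about 95% power, and 130 in total at SD 39.4 gives about 34%.

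**Step 6: totals that would give 90% power.** At SD 39.4: 512 evaluable; 512 / 0.9 = 569, or 570 for equal groups. At SD 26: 224 evaluable; 224 / 0.9 = 249, or 250 for equal groups. With the protocol's own rounded allowance (255 to 300, 112 to 130), the doubled totals are 600 and 260.

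**The case against.** The section never prints a word such as total or per arm, so 300 and 130 might themselves be unlabelled per-group targets. On that reading 300 per arm less 10% leaves 270 per arm, and power at SD 39.4 is 91.5%, so the calculation would be sound and only the label missing. This cannot be excluded. However, a target sample size given in patients for a study is ordinarily read as the whole trial, and nothing in the document mentions 600 or 260 patients. Even on this reading the text needs correcting, because recruitment is then ambiguous by a factor of two.

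A second objection is that 65% for 300 patients applies only at the worst-case SD. At the SD of 26, which the section also reports, 300 in total has about 95% power. That is true and should be disclosed. It does not rescue the claim as written: the 300 was derived from SD 39.4, and the target that was derived from SD 26 is 130, which also falls to about 65%.

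Third, the calculation compares mean healing times, whereas the statistical section plans Kaplan-Meier curves. Neither 90% nor 65% is strictly the power of that comparison. This limits what the figures mean: they show that the section disagrees with itself on its own method. It leaves that disagreement in place.

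**Conclusion.** The concern holds. The figures 42, 255 and 112 are sizes for one arm, and the targets built on 255 and 112 are presented as patient numbers for a two-arm trial without doubling. At the SD from which each target was derived, power is about 65% after the protocol's 10% dropout (63% to 70% across the loss assumptions tried), against the stated 90%. The chance of missing the target effect is about 35% instead of 10%.

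This rests on three assumptions: a two-sided test, which is inferred because it reproduces all three figures; 1:1 allocation, which is not stated (at a fixed total and equal SDs, unequal allocation would lower power); and reading 300 and 130 as trial totals. If they were meant per arm, the power claim stands and the error is an unlabelled figure that understates recruitment by half. A correction is required before the power statement can be relied on.

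**What to change.** In the sample size section, label 42, 255 and 112 as per group, and state the two-sided alpha and the allocation ratio. Then choose one of these:

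- **Keep 300 as the total.** Restate power as about 65% at SD 39.4 and about 95% at SD 26, both after 10% dropout, or state that 90% power at SD 39.4 applies to a 15.5-day difference. If 130 is the intended total, the corresponding power is about 65% at SD 26 and about 34% at SD 39.4.
- **If the targets were meant per arm,** write 300 per arm and 600 in total, or 130 per arm and 260 in total.
- **To hold 90% power with only the 10% dropout allowance,** the total is about 570 at SD 39.4 or 250 at SD 26.

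Whichever is chosen, name one target, so that the stated power and the total number of patients agree. Restating the power costs one paragraph and a less favourable figure, with no extra patients. Holding 90% power at SD 39.4 with a total above 300 means recruiting nearly twice as many patients.
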